12.0 TREATMENT/FOLLOW-UP DECISION AT EVALUATION OF PATIENT

12.1 No disease progression or Unacceptable Adverse Events

Patients who have not had disease progression and have not developed unacceptable toxicity will be eligible for re-treatment at their current dose level until disease progression, unacceptable toxicity, or refusal.

12.2 No disease Progression, Unacceptable Adverse Events

Those patients who have not had disease progression, but have experienced unacceptable toxicity may be eligible for retreatment at a lower dose (see [Section 8.0](#)).

12.3 Discontinuation of Protocol Therapy

Reasons why the protocol therapy may be discontinued:

- Tumor progression
- Request by the patient to withdraw
- Unacceptable toxicity
- Inter-current illness
- Administration of alternative treatment

Arm 1 patients:

Patients who discontinue treatment for any of the above reasons will proceed to event monitoring. Patients will be followed yearly for a maximum of 5 years from study registration. Once a patient has discontinued study treatment, future therapy is at the discretion of the treating physician.

Arm 2 patients:

Patients randomized to tamoxifen who progress during tamoxifen treatment may choose to switch to Z-Endoxifen HCl and continue on Z-Endoxifen HCl until disease progression is noted. After disease progression during Z-Endoxifen HCl treatment patient will proceed to event monitoring. Patients will be followed yearly for a maximum of 5 years from study registration. Once a patient has discontinued study treatment, future therapy is at the discretion of the treating physician.

Patients who discontinue treatment for any of the above reasons other than progression or patients who refuse to crossover to Z-Endoxifen HCl will proceed to event monitoring. Patients will be followed yearly for a maximum of 5 years from study registration/randomization. Once a patient has discontinued study treatment, future therapy is at the discretion of the treating physician.

12.4 Refuse to begin protocol treatment following randomization

If an eligible patient refuses to begin treatment following randomization (and is classified as a cancel by the Research Base), all on-study materials and the End of Active Treatment/Cancel Notification Form must be submitted. For those patients who also consent to the correlative studies, research biospecimens are not to be submitted. No further data submission is necessary. Future therapy is at the discretion of the treating physician.

12.5 Ineligible prior to the start of protocol treatment

If a patient is determined not to have satisfied each and every eligibility criteria for study entry after randomization but prior to the start of protocol treatment, on-study materials must be submitted. For those patients who also consent to the correlative studies, research biospecimens are not to be submitted. Bio-specimens should not be submitted. No further data submission is necessary. Future therapy is at the discretion of the treating physician.

12.6 Ineligible after to the start of protocol treatment

If a patient is determined not to have satisfied each and every eligibility criteria but has received some study treatment and is having some clinical benefit, the patient may be able to continue study treatment per protocol after consultation with the study chair. If the patient does continue on study treatment, study forms and bio-specimens should be submitted using the same schedule as eligible patients. If the patient does not continue study treatment, the patient will go into event monitoring phase for a maximum of 5 years post randomization. Future therapy is at the discretion of the treating physician.

12.7 Extraordinary Medical Circumstances

If, at any time the constraints of this protocol are detrimental to the patient's health and/or the patient no longer wishes to continue protocol therapy, protocol therapy shall be discontinued. In this event:

- Document the reason(s) for discontinuation of therapy on data forms.
- Follow the patient for protocol endpoints as required by the Study Calendar.

13.0 STATISTICAL CONSIDERATIONS**13.1 Study Design**

A randomized phase II clinical trial design was chosen to assess whether Z-Endoxifen HCl shows promise in providing greater in antitumor activity (in terms of increasing progression-free survival) than tamoxifen in postmenopausal women with metastatic ER positive breast cancer that is endocrine resistant.

This study will use a dynamic allocation procedure to allocate an equal number of patients to each of the treatment arm. This procedure will balance the marginal distributions of the stratification factors between these treatment arms. The stratification factors that will be used are: prior palbociclib and/or everolimus, type of disease and degree of endocrine resistance (see Section [4.8](#)).

All patients meeting the eligibility criteria who have signed a consent form and have begun treatment will be evaluable for assessment of all of the clinical endpoints. Patients will be included in the treatment group they were randomized to regardless of their actual treatment or duration of treatment. Summary statistics for patient and tumor characteristics, eligibility rates, length of follow-up, and treatment acceptance rates will be calculated by assigned treatment arm.

13.1.2 Definition and documentation of primary endpoint.

The primary endpoint is progression-free survival (PFS) defined as the time from randomization to documentation of local, regional or distant disease progression or death without progression of disease.

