2.2 Secondary Objectives

- 2.2.1 To assess the safety profile of each of these agents in this patient population.
- 2.2.2 To assess whether the tumor response rate (as determined using the RECIST criteria) among those randomized to Z-endoxifen HCl differs from that among those randomized to tamoxifen.
- 2.2.3 To estimate the median progression-free survival time for those who receive Z-Endoxifen HCl after disease progression with tamoxifen.

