13.1.6 Secondary Clinical Endpoints

13.1.6.1 Adverse Events

Per CTEP Version 4.0 of the NCI CTCAE, an adverse event (AE) is any unfavorable and unintended sign (including an abnormal laboratory finding), symptom, or disease temporally associated with the use of a medical treatment or procedure that may or may not be considered related to the medical treatment or procedure. All grade 2, 3, 4 or 5 adverse events will be documented and assigned an attribute by treating clinician as to its relationship to treatment.

Note: Serious adverse events will be reported on CTEP-AERS using CTCAE v5.0.

For a given AE, the proportion of patients on each treatment arm who report developing a grade 2-5 of this AE will be determined.

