13.1.6.2 Tumor Response Rate by study arm

The tumor response rate is defined as the 100% time the number of patients with a CR or PR (as defined by the RECIST criteria) on 2 consecutive evaluations at least 6 weeks apart divided by the total number of eligible patients who began study treatment. A 90% binomial confidence interval will be constructed for the true response rate.

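### The one evaluable set in 13.1 leaves patients who took study drug and were later found ineligible out of the adverse-event proportions; a safety set of all treated patients should be named

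*Combined protocol and SAP*

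**What the plan says.** Section 13.1 sets one evaluable set for the whole trial: "All patients meeting the eligibility criteria who have signed a consent form and have begun treatment will be evaluable for assessment of all" (every clinical endpoint). The next sentence deals with arm assignment: "Patients will be included in the treatment group they were randomized to regardless of their actual treatment or duration of treatment". It settles which arm a patient is counted in. It does not bring back a patient who fails the eligibility condition.

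Section 13.1.6 is headed "Secondary Clinical Endpoints", and its first entry, 13.1.6.1, is adverse events. The summary there is that "the proportion of patients on each treatment arm who report developing a grade 2-5 of this AE will be determined". It states no denominator of its own. The next entry, tumor response in 13.1.6.2, does state one: "divided by the total number of eligible patients who began study treatment". Safety is secondary objective 2.2.1: "To assess the safety profile of each of these agents in this patient population". No safety or all-treated population is defined in the documents.

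Section 12.6 provides for a patient found ineligible after dosing. If she "has received some study treatment and is having some clinical benefit, the patient may be able to continue study treatment per protocol", then "study forms and bio-specimens should be submitted using the same schedule as eligible patients". If she does not continue, she moves to event monitoring, which the notes to the Schema describe as notification of progression, a new primary or death.

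The safety stopping rule in 13.1.7 is framed on patients randomized to an arm and has no eligibility condition.

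**The concern.** An AE rate is meant to describe what happens to people who take the drug. Removing someone from it because of a finding made after she was dosed discards real exposure and real toxicity. In this trial drug supply is open label (10.1.1), so the finding could be made by people who know both the arm and the outcome.

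Some eligibility criteria overlap with known risks. A recent DVT or PE is excluded (3.2.13), and thromboembolic event is a listed Z-Endoxifen HCl risk (9.3). Platelet and AST limits apply at entry (3.2.17), and both laboratory changes are also listed risks. Patients who fail such criteria need not have the same toxicity rate as eligible patients.

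At stake is the descriptive safety profile in 2.2.1, with about 40 patients per arm. Common events would move by a few percentage points at most. A rare severe event could appear in the monitoring count under 13.1.7 and be missing from the final AE table.

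**Working it through.** **Inputs**
- Planned eligible patients: 80, or 40 per arm (13.1.3). Under 13.1 this is also the planned AE denominator.
- Patients treated and later found ineligible, m per arm: not given. Assumed m = 0 to 2.
- Illustrative AE count among eligible patients, x: 4 of 40, chosen for the example.
- AE count among the m excluded patients, k: unknown, from 0 to m.

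**The plan's own figures**
- Events by Schoenfeld's formula, hazard ratio 0.50, one-sided alpha 0.10, power 95%: 4 × (1.2816 + 1.6449)² / (ln 0.5)² = 71.3, rounded up to 72. The plan states 72.
- Screening: 80 / (1 − 0.30) = 114.3, rounded up to 115. The plan states 115.

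Both reproduce. Neither depends on the AE analysis set, so a change to that set leaves them as they are.

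**Does the 30% apply here?** No. The 24 of 81 in 13.1.3 (29.6%) were ineligible on pathology. Under 4.5, a patient whose biopsy does not confirm ER-positive, HER2-negative disease does not go on to registration or randomization, so she normally takes no drug. The figure says nothing about m.

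**Effect on an AE proportion**
- Rate as planned: x / 40.
- Rate in all treated patients: (x + k) / (40 + m).
- The second exceeds the first only if k/m is greater than x/40, that is, if the excluded patients had the event more often than the eligible ones.

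| m per arm | k | All treated | Rate |
|---|---|---|---|
| 0 | 0 | 4/40 | 10.0% |
| 1 | 0 | 4/41 | 9.8% |
| 1 | 1 | 5/41 | 12.2% |
| 2 | 0 | 4/42 | 9.5% |
| 2 | 1 | 5/42 | 11.9% |
| 2 | 2 | 6/42 | 14.3% |

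The range over m = 0 to 2 is 9.5% to 14.3%, which lies on both sides of 10.0%.

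**Rare event.** With 0/40 among eligible patients, one excluded patient with the event gives 1/41 = 2.4%, and two give 2/42 = 4.8%. A reported zero would in fact be one or two.

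**The case against.** The strongest reply is textual. Section 13.1 says who will be evaluable. It does not say that only these patients will be, and nowhere does it say that treated ineligible patients are dropped from safety. Section 13.1.6.1 refers to patients by arm with no eligibility condition, while 13.1.6.2 states the condition for response. If the general sentence already fixed every denominator, 13.1.6.2 would not need to repeat it. This shows that the restriction on AEs is not explicit. It does not create a safety set: the general sentence covers every clinical endpoint, AEs are filed as one, and no other population is available.

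Several other objections stand and limit the point:
- Section 12.6 is a contingency clause. It gives no count and does not show that such patients are expected.
- History, physical and laboratory work fall within 14 days before pre-registration (5.0), so most safety-related ineligibility should surface before dosing.
- Serious events go through expedited reporting with no eligibility filter, and deaths on study need both routine and expedited reports (9.2). The monitoring board receives AE data twice a year (13.1.7).
- Both study calendars already place an AE assessment at progression or discontinuation (5.1, 5.2), and 12.6 does not waive it.
- The stopping rule concerns treatment-related grade 4 events and the AE summary concerns grades 2 to 5. Different populations for the two are untidy but not in themselves a contradiction.

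**Conclusion.** The point holds as a weakness in the definition of the analysis set. Followed as written, the plan reports AE proportions without patients who were exposed and later found ineligible, although forms are collected for those who continue and the monitoring rule has no such limit. On the assumption of 0 to 2 such patients per arm, a 10.0% rate could lie between 9.5% and 14.3%. For a rare serious event, one patient can decide between none reported and one. The number is probably small, and the primary analysis is untouched.

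The documents do not support stronger readings that a reader might infer:
- **That reported safety is biased toward fewer events.** The direction depends on the unknown AE rate in the excluded patients, and the range runs both ways.
- **That about 30% of treated patients would be lost.** That figure is pathology ineligibility, normally acted on before randomization.
- **That a serious event would vanish.** It could be missing from the AE table, but it would still reach expedited reporting and the monitoring board.
- **That every exclusion criterion marks higher toxicity.** For strong CYP2D6 inhibitors, 10.2.5 links inhibition on tamoxifen to lower endoxifen levels and suggests that this may explain improvement in hot flashes, so that criterion does not help the argument.

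**What to change.** - In 13.1, limit the eligible-and-treated rule to the efficacy endpoints.
- In 13.1.6.1, state that AE proportions are calculated in all patients who received at least one dose of study drug, whatever their eligibility status, and show eligible patients as a sensitivity row.
- In 12.6, confirm that the AE assessment at discontinuation already in the calendars (5.1, 5.2) applies to patients who stop under that section. This is a confirmation, not a new collection requirement.

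The cost is a sentence or two of text and one extra row per AE table. For patients who continue under 12.6 the forms are already submitted. The 80 eligible patients, the 72 events and the power stay the same. This is a cheap improvement.

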13.1.3 Sample Size, Accrual Time and Study Duration

This trial was designed under the assumption that the median progression-free survival time among patients receiving tamoxifen is 3.0 months. Disease assessments in this trial are made at a frequency that is half the hypothesized median of the tamoxifen arm. Stone et al [41, 42] (2, 3) found that when disease assessments are made at a frequency that is half the control median, the difference in power between the log-rank test (with documented progression times) and generalized log-test with interval censored data was < 3%. As such we will determine the sample size assuming a log-rank test will be used with one-sided alpha=0.10 and power=95% so that the interval censored approach with the generalized log-rank test will have a power of > 90%.

With a sample size of 80 eligible patients (40 per treatment arm randomized in equal numbers) over a 15 month period and followed at least another 9 months after the close of enrollment before analysis is undertaken, a one-sided alpha=0.10 generalized log-rank test will have at least a 90% chance of detecting a 50% decrease in hazard of disease progression with Z-Endoxifen HCl relative to tamoxifen.

That corresponds to being able to detect an increase in the median PFS time from 3.0 months with tamoxifen to 6.0 months with Z-Endoxifen HCl.

An additional 14 patients will be screened to account for ineligible patients (tumors that are ER negative on biopsy) and those who cancel participation prior to starting treatment.

As of November 1, 2016, 24 (30%) of the 81 patients enrolled on this trial were found to have ER negative and/or HER2 positive breast cancer, a second primary cancer, or benign disease, making them ineligible. Therefore, the number of patients needed to be screened to obtain 80 eligible patients will be increased from 94 to 115 patients.

The efficacy analysis will be conducted when at least 72 patients have provided documentation of local, regional or distant disease progression or death without progression of disease.

13.1.3.1 Study duration

It is anticipated that the enrollment period will be 15 months and the minimum follow-up period after the close of enrollment will 9 months, and an additional 3 months will be required to complete data submissions and curate the study data. Thus, it is anticipated that primary efficacy analysis will begin approximately 27 months after the trial is activated.

13.1.4 Interim efficacy/futility analysis plan

No formal interim efficacy/futility analysis is planned as the enrollment would be complete when 50% of the events will have occurred.

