1.3.5 PI3K/mTOR pathway in endocrine resistant breast cancer

Activation of the phosphatidylinositol 3-kinase (PI3K)/AKT/mammalian target of rapamycin (mTOR) pathway has been extensively linked to the development of endocrine resistance in ER positive breast cancer. Specifically, cross-talk between ER signaling pathways and the PI3K/AKT/mTOR pathway is associated with the development of endocrine resistance when ER positive cells undergo long term estrogen deprivation (LTED) mimicking AI resistance [24]. These observations have led to the development of clinical studies which have demonstrated that in patients with acquired endocrine resistance, the addition of an mTOR inhibitor to hormonal therapy prolonged PFS [25, 26].

Bachelot et al randomized postmenopausal women with hormone receptor-positive, human epidermal growth factor receptor 2-negative, AI-resistant metastatic breast cancer to either tamoxifen 20 mg/d plus everolimus 10 mg/d ($n = 54$) or tamoxifen 20 mg/d alone ($n = 57$) (randomized phase II). Randomization was stratified by primary and secondary hormone resistance. Primary end point was clinical benefit rate (CBR), defined as the percentage of all patients with a complete or partial response or stable disease at 6 months. The 6-month CBR was 61% (95% CI, 47 to 74) with tamoxifen plus everolimus and 42% (95% CI, 29 to 56) with tamoxifen alone. Time to progression (TTP) increased from 4.5 months with tamoxifen alone to 8.6 months with tamoxifen plus everolimus, corresponding to a 46% reduction in risk of progression with the combination (hazard ratio [HR], 0.54; 95% CI, 0.36 to 0.81). Risk of death was reduced by 55% with tamoxifen plus everolimus versus tamoxifen alone (HR, 0.45; 95% CI, 0.24 to 0.81).

The main toxicities associated with tamoxifen plus everolimus were fatigue (72% v 53% with tamoxifen alone), stomatitis (56% v 7%), rash (44% v 7%), anorexia (43% v 18%), and diarrhea (39% v 11%).

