1.3.6 Summary of available treatments for ER+ breast cancer that is AI refractory

In summary, for women with ER+ positive breast cancer, nonsteroidal AI's are the standard of care. However, in patients with disease refractory to non-steroidal AI's, the FDA approved treatments most commonly utilized include fulvestrant, exemestane, or exemestane + everolimus. The time to progression for single agent tamoxifen in patients with AI refractory breast cancer is similar to exemestane or fulvestrant (range 4-7 months). Everolimus containing regimens result in the most impressive PFS rates (8-10 months); however, the toxicity of everolimus containing regimens (fatigue, stomatitis, pneumonitis, diarrhea, anorexia) are substantial for some patients, leading to treatment discontinuation in 9% of patients enrolled onto BOLERO-2 [28]. In all cases, these drugs simply prolong PFS and resistance develops in all cases. New strategies are therefore needed.

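### Does the reason given in Section 13.1.4 for having no interim analysis need correcting?

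*Combined protocol and SAP*

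**What the plan says.** Section 13.1.4 is one sentence: "No formal interim efficacy/futility analysis is planned as the enrollment would be complete when 50% of the events will have occurred". It shows no projection of events against enrollment.

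The relevant inputs are in Section 13.1.3:

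- Size and accrual: "With a sample size of 80 eligible patients (40 per treatment arm randomized in equal numbers) over a 15 month period", with at least 9 further months of follow-up.
- Target effect: "an increase in the median PFS time from 3.0 months with tamoxifen to 6.0 months with Z-Endoxifen HCl", a hazard ratio (HR) of 0.5.
- Trigger: "The efficacy analysis will be conducted when at least 72 patients have provided documentation" of progression or death.

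Section 13.1.3.1 repeats the 15 months and adds that "an additional 3 months will be required to complete data submissions and curate the study data". Neither section says whether patients arrive evenly, slowly at first, or otherwise. Section 13.1.2 times PFS to documented progression, so an event can be counted only once it has been seen and recorded.

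**The concern.** The sentence is the only justification offered for running a randomized trial of an investigational agent without a formal efficacy or futility look. A reader who takes the plan's own medians and spreads 80 patients evenly over 15 months finds that half of the events arrive while patients are still being enrolled. The shortfall is larger if endoxifen has no advantage, which is the case where a futility look would matter most. If the stated reason fails, the decision appears to have no support, and some patients might be randomized after the data could have shown that continuing was unpromising.

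**Working it through.** **Reproducing the plan's event target.** With HR 0.5, one-sided alpha 0.10 and 95% power, the Schoenfeld formula gives 4 × (1.2816 + 1.6449)² / (ln 2)² = 71.3, rounded up to 72. This matches Section 13.1.3. Half is 36.

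**Assumptions that are mine, not the plan's.** Exponential PFS, uniform entry over 15 months, no dropout.

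**Exact progression times.** For t up to 15 months, expected events per arm are 40 × [t − (1 − e^(−Lt))/L] / 15, with L = ln 2 / median. At t = 12.03:

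- Tamoxifen (L = 0.2310): 40 × (12.03 − 4.06)/15 = 21.3
- Z-Endoxifen (L = 0.1155): 40 × (12.03 − 6.50)/15 = 14.7

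The sum is 36.0, with 80 × 12.03/15 = 64 enrolled. At month 15 the same formula gives 28.8 + 21.0 = 49.8 events, or 69% of 72.

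**Progression counted at scans.** This is closer to what the plan counts. Each progression moves to the next scheduled scan s_k, so expected events per arm are (40/15) × Σ P(s_(k−1) < T ≤ s_k) × (t − s_k), summed over scans up to t. The study calendar (Section 5.1, note E) puts scans at weeks 6, 12 and 18, then every 12 weeks. At t = 13.07 months this gives 21.3 + 14.7 = 36.0. Section 11.1 adds a week-24 scan before moving to 12-week intervals, which changes little.

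| Uniform accrual, 36 events | Month | Enrolled of 80 |
|---|---|---|
| HR 0.5, exact times | 12.0 | 64 |
| HR 0.5, at scans | 13.0–13.1 | 69–70 |
| HR 1 (both medians 3.0), exact times | 10.7 | 57 |
| HR 1, at scans | 11.6–11.7 | 62 |

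In 20,000 simulated trials with HR 0.5 and scan timing, the 36th event came before the last enrollment in 97–98% of runs. So under even accrual the sentence does not hold.

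**Conditions under which it does hold or nearly holds (scan timing).**

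- *Rising accrual.* If cumulative entry is proportional to t², 36 events fall at month 15.4–15.5 under HR 0.5, after enrollment closes. All 80 were already enrolled in about 71–76% of simulated trials. Under HR 1 the month is 14.3–14.4, with 80 × (14.3 to 14.4 / 15)² = about 73–74 enrolled.
- *Delay between scan and usable record.* Two months added to 13.0–13.1 gives 15.0–15.1, so enrollment is essentially complete under HR 0.5. Under HR 1, 11.7 + 2 = 13.7 months, or 73 enrolled; with 3 months, 14.7 months, or 78. The plan allows 3 months at the final analysis; applying 2 or 3 months to an interim look is an assumption.
- *Longer control median.* At 4.5 months on tamoxifen, 79–80 are enrolled under HR 0.5 and 70–71 under HR 1. Section 1.3.5 reports such a value: "Time to progression (TTP) increased from 4.5 months with tamoxifen alone to 8.6 months with tamoxifen plus everolimus". The design itself uses 3.0.
- *Meaning of enrollment.* Section 13.1.3 says "As of November 1, 2016, 24 (30%) of the 81 patients enrolled on this trial were found" to be ineligible, so its use of the word takes in patients who failed the pre-registration checks. Section 3.3 allows up to 28 days (0.92 months) from pre-registration to registration. If the 15 months run on pre-registration, 36 events move to at most 13.07 + 0.92 = 13.99 months, when 75 of the 80 have entered (HR 0.5). Under HR 1, 11.70 + 0.92 = 12.62 months gives 67.

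**The case for a change.** The strongest opposing case is that the plan should not borrow conditions it does not state. It designs on 3.0 months, so a 4.5-month median cannot be used to rescue this sentence. It speaks of events having occurred, so reporting delay is not the reason written. Even a linear ramp leaves the sentence short under HR 1. Before any delay, 80 − 62 = 18 patients would still be to come in that case, and rewording would cost only a sentence or two.

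Most of this stands. The sentence does not follow from the Section 13.1.3 inputs without an added condition, and the documents name none. Two parts do not stand. First, the absence of a stated pattern cuts both ways: uniform accrual is the reader's choice, so the plan has not been shown to contradict its own figures. The expected 71.9 events at month 24 under uniform accrual with exact times does not settle the matter, because scan counting gives 70.1 and 72 comes from the power formula. Second, any reworded rationale would still end with no interim analysis. It would rest on the fact that most patients are enrolled by the time 36 documented events can be analyzed, which is close to what Section 13.1.4 already says.

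**Conclusion.** The rationale is looser than it reads, but no change follows because nothing would be gained. Under uniform accrual, exponential PFS, the design medians and scan timing, 10–11 of 80 patients remain to be enrolled at half the events, and about 18 if there is no effect. With two months of data delay those numbers fall to about 0 and 7 in expectation. None of this shows that an interim analysis was required, and the 72-event analysis and its error rates do not depend on the sentence.

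Safeguards exist without a formal look. Section 13.1.7 sends accrual, adverse-event and efficacy data to the monitoring board twice a year, and Section 13.1.8 allows earlier termination in light of toxicity, treatment failure or new science. The sponsor also holds the real accrual record: at November 1, 2016, 81 − 24 = 57 patients remained after the ineligible were removed. That record supersedes any assumed pattern. Adding a futility look would be a separate design choice, not a correction of this sentence.
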